13.1.4 Efficacy Analysis

The ITT population will be used as the primary population for the primary analysis of efficacy at Day 90. Select efficacy analyses will be repeated as secondary analyses in the ITT and PP populations for the Double-blind Period. Efficacy analyses will also be repeated in the OLE using the OLE ITT, OLE mITT, and OLE PP populations. No formal inferential analyses will be conducted for efficacy variables in the OLE.

Efficacy endpoints will be based on investigator assessment.

13.1.4.1 Efficacy Endpoints

Primary efficacy endpoint: The proportion of subjects in each treatment group who experience successful resolution of LI where “success” is defined as clear/almost clear overall and at least a 2-grade change from Baseline at Day 90/EOT in the Double-blind Period on the 5-point IGA scale.

Secondary: The secondary endpoints are as follow:

- The difference in mean scores between the active trifarotene cream HE1 and vehicle groups in the following assessment indices from Baseline through Day 90:
 - 5-point VIIS scale for scaling
 - Individual score for roughness (Scale: 0–4)
 - Palm/sole Assessment (Scale: 0–4)
 - Quality of life per DLQI and cDLQI
- The difference in proportion of subjects with presence of fissures on palm/soles (presence/absence, number of fissures, and pain associated with fissures [on a 0-3 scale]) at Day 90 between the active trifarotene cream HE1 and vehicle groups

Exploratory: The exploratory endpoints are as follow:

- The difference in mean ectropion scores (ESS of 0–8) between the active trifarotene cream HE1 and vehicle groups from Baseline through Day 90
- The difference in quality of life per EQ-5D-5L and EQ-5D-Y scores between the active trifarotene cream HE1 and vehicle groups from Baseline through Day 90

13.1.4.2 Primary Analysis

For the Double-blind Period only, the number and proportion of subjects in each treatment group with successful resolution of LI by Day 90/EOT will be presented. The primary efficacy endpoint will be analyzed using a logistic regression model with treatment and age group as factors. Other baseline characteristics and interactions may be included. The odds ratios and 95% CIs for the

odds ratios will be presented. The difference in proportions between the active trifarotene cream HEI and vehicle cream group, 95% CIs for the differences, and P-values for the differences in treatment will also be presented.

Descriptive summaries (such as mean, standard error, median, minimum, and maximum) and the changes from baseline will be provided for IGA scores for both periods.

13.1.4.3 Secondary Analyses

Secondary and exploratory efficacy endpoints will be analyzed separately for each period (Double-blind and OLE) using descriptive statistics.

Additionally, for the Double-blind Period only, change from Baseline in continuous secondary endpoints through Day 90 will be presented and analyzed using a mixed model for repeated measures (MMRM). The model will include the change from baseline score as the dependent variable, treatment group as a fixed effect, subject as a random effect, and baseline score value as a covariate.

For subjects who report having fissures, descriptive summaries of the number of fissures and pain related to fissures will also be presented by treatment group and body area for each period.

The DLQI scores will also be analyzed using descriptive statistics through Day 90.

The proportion of subjects with at least a 50% reduction in IGA score from Baseline will be analyzed using the same logistic regression analysis described in Section [13.1.4.2](#).

13.1.4.4 Exploratory Analyses

Descriptive summaries and the changes from baseline will be provided for ectropion scores and EQ-5D-5L scores by visit for each period. No formal inferential analyses will be conducted for exploratory endpoints.

13.1.4.5 Corroborative, Sensitivity, and Other Analyses

To assess the effect of missing data on the primary efficacy analysis, a sensitivity analysis will be performed using multiple imputation (MI) for the Double-blind Period only. Multiple-imputations will be used to replace missing IGA outcomes using multiple draws from the posterior predictive distribution estimated from the treatment groups. IGA scores will be imputed and then categorized as treatment success according to Section [13.1.4.1](#). Imputation will not be performed for the OLE. Full details will be specified in the SAP.

Thorough assessment on the extent of missing data and procedural adjustments due to COVID-19 as it pertains to the primary and secondary efficacy endpoints will be conducted ahead of database lock, and additional sensitivity analyses may be performed. Full details will be documented in the SAP.

The proportion of subjects who experience a 2-grade change from baseline to Day 90 in individual score for roughness and palm/sole assessment will also be explored using a logistic regression model with treatment and age group as factors. Other baseline characteristics and interactions may be included. The odds ratios and 95% CIs for the odds ratios will be presented. The difference in

proportions between the active trifarotene cream HEI and vehicle cream group and the 95% CIs for the differences will be presented.

For analyses involving study site, if the number of subjects per site is small, sites may be pooled for safety and efficacy analysis or omitted from statistical models as the anticipated number of subjects per site is small, treatment is self-administered, and the sites are using standardized procedures for all assessments. If the distribution of enrollments at sites is such that one or few are enrolling a majority of subjects, a subgroup analysis by site may be performed. The final determination will be made prior to database lock.

Details of these analyses will be further detailed in the SAP.

13.1.5 Clinical Pharmacology Analyses

13.1.5.1 Pharmacokinetics

For noncompartmental analysis, plasma concentrations will be listed and summarized at each time point using descriptive statistics. Descriptive statistics reported will include the arithmetic mean, SD, CV%, geometric mean, minimum, maximum, and median. Only the range and the median will be reported for T_{max} , as this is a categorical parameter. The PK parameters will also be summarized by treatment using descriptive statistics.

Individual plasma concentration plots and mean data graphs will be produced using both linear and semi-logarithmic scales. Mean data graphs will show plasma concentration profiles by treatment group.

Pharmacokinetic plasma parameter estimates and summaries will be completed for the subjects in the PK population. Testing of PK parameters will be outlined in the SAP.

13.1.6 Safety and Tolerability Analyses

Safety analyses through Day 90 of the Double-blind Period will be conducted using data from the Safety Population and safety analyses in the OLE will be conducted using the OLE Safety Population (as defined in Section 13.1.1). Safety variables include treatment-emergent AEs, clinical laboratory values, vital signs, ECG readings, and physical examination results. No formal inferential analyses will be conducted for safety variables in either period.

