13.1.6.2 Adverse Events

All AEs will be coded using the Medical Dictionary for Regulatory Activities (MedDRA), Version 20.1 or higher.

Treatment-emergent AEs are defined as:

- AEs with onset at the time of or following the start of treatment with IP through the Follow-up Visit or Early Termination Visit, whichever occurs first, or
- AEs starting prior to the start of treatment but increasing in severity or relationship at the time of, or following, the start of treatment with IP through the Follow-up Visit or Early Termination Visit, whichever occurs first.

The number and percentage of subjects with AEs will be displayed by each treatment group in the Double-blind Period and overall in the OLE by system organ class and preferred term. Summaries of AEs by severity and relationship to IP will also be provided. Serious adverse events and AEs resulting in discontinuation of IP will be summarized separately in a similar manner. Subject listings of AEs, SAEs, and AEs causing discontinuation of IP will be produced.

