2. PROTOCOL SUMMARY

2.1. Synopsis

PRODUCT NAME/NUMBER	Trifarotene (CD5789) Cream HE1
PROTOCOL NUMBER	18-ICH-001
EUDRACT NUMBER	2018-003272-12
DEVELOPMENT PHASE	2
PROTOCOL TITLE	A Phase 2 Randomized, Multicenter, Double-blind, Vehicle-controlled, 12-Week, Safety, and Efficacy, and Systemic Exposure Study followed by a 12-Week Open-label Extension of Trifarotene (CD5789) Cream HE1 in Subjects with Autosomal Recessive Ichthyosis with Lamellar Scale
INDICATION	Lamellar ichthyosis
OBJECTIVES	
Primary: To compare the safety and efficacy of 2 concentrations of trifarotene cream HE1 versus vehicle in subjects with moderate to severe autosomal recessive ichthyosis with lamellar scale, also known as lamellar ichthyosis (LI) after 12 weeks of treatment.
 
Secondary:
 
 To assess systemic exposure to trifarotene and its major metabolites after topical application of the investigational product (IP) on up to 90% body surface area (BSA) twice weekly. To assess safety for up to 24 weeks of dosing with open-label trifarotene cream HE1 200 µg/g.

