5.3. Summary of Potential Risks and Benefits

Although the primary objective of this study is safety in the patient population with LI, the potential benefits of study participation are that subjects with LI may experience a reduction in their LI symptoms as a result of treatment with trifarotene (CD5789) cream HE1. No other benefits of participation are anticipated.

The potential risks of study participation include those associated with exposure to trifarotene (CD5789) cream HE1 and the risks of medical evaluation, including venipuncture.

Animal studies with CD5789 have shown reproductive toxicity in the embryo-fetal studies. Despite low systemic levels with the CD5789 concentration of 50 µg/g used in patients with acne, CD5789 must not be administered during pregnancy.

When CD5789 is used in the other formulations and/or for other indications and/or with higher concentrations or higher application surface areas, the potential risk of teratogenicity needs to be considered as the safety margin may be lower. Depending on the study population and conditions mentioned above, or other specific requirements, the appropriate contraception method is described in this protocol.

It is unknown whether CD5789 or its metabolites are excreted in human milk. A risk to the newborns/infants cannot be excluded. Lactating women are not eligible for the clinical study.

Certain cutaneous signs and symptoms of irritation and localized reactions at the application site such as erythema, scaling, dryness, stinging/burning, and pruritus may be experienced with use of CD5789. Depending upon the severity of these side effects, subjects may be instructed to reduce the frequency of application or to discontinue use.

Trifarotene cream contains propylene glycol that is mildly irritant to the skin, eyes, and mucous membranes. Trifarotene (CD5789) cream HE1 also contains butylated hydroxytoluene that may cause local skin reactions (e.g., contact dermatitis), or irritation to the eyes and mucous membranes and sodium benzoate that is mildly irritant to the skin, eyes, and mucous membranes.

CD 5789 is mildly irritant to the skin, eyes, and mucous membranes. Therefore, it should not come into contact with the eyes, mouth, or mucous membranes.

There is a potential risk of skin sensitization. If a reaction suggesting sensitivity to trifarotene (CD5789) cream HE1 occurs, the use of the trifarotene cream HE1 must be discontinued.

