6. OBJECTIVES

6.1. Primary Objective

The primary objective is to compare the safety and efficacy of 2 concentrations of trifarotene cream HE1 versus vehicle in subjects with moderate to severe autosomal recessive ichthyosis with lamellar scale, also known as lamellar ichthyosis (LI) after 12 weeks of treatment.

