7. STUDY DESIGN

7.1. Overall Study Design and Plan

The first part of this study is a phase 2, randomized, 2-cohort, double-blind, vehicle-controlled, multicenter study of the safety, tolerability, PK, and efficacy study of trifarotene cream HE1 100 µg/g and 200 µg/g in subjects with LI. Subjects who complete the randomized, double-blind, vehicle-controlled period of the study will be eligible to continue into an open-label extension (OLE) and be treated with trifarotene cream HE1 200 µg/g for an additional 12 weeks.

The randomized, double-blind, vehicle-controlled period of the study in subjects with moderate to severe LI (i.e., 3–4 on a 5-point Investigator Global Assessment [IGA] scale where 0 = clear; 1 = almost clear; 2 = mild; 3 = moderate; and 4 = severe, is designed to compare the safety of 2 doses of trifarotene cream HE1 with that of vehicle in the treatment of LI.

Upon signing informed consent and entering the Screening Period, subjects will stop using physical and medical treatments for LI, including balneotherapy, and may begin to washout prohibited topical and systemic treatments with designated washout periods (Table 9-1), as applicable. Washout may be up to 3 months, as necessary.

During washout, subjects may continue taking usual care of visible skin (face and scalp) for cosmetic reasons and of extremities (hands and feet) to avoid functional consequences on walking or moving their fingers. Subjects may shower, but not bathe or swim. The IGA will be evaluated on the rest of the body at Baseline. After completing any necessary washout of prohibited medications, subjects will return to the site to complete the study eligibility requirements.

The first cohort of subjects (Cohort A) will randomize approximately 15 subjects in a 1:1:1 ratio to trifarotene (CD5789) cream HE1 100 µg/g, trifarotene cream HE1 200 µg/g, or vehicle.

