11.3. Special Considerations

11.3.1 Adverse Events of Special Interest

Since topical retinoids are associated with local application site AEs, particularly when beginning treatment, these events will be followed closely during the study and considered AEs of special interest (AESIs).

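### Safety versus vehicle is part of the primary objective, but Section 13.1.6 plans only by-arm summaries, with no between-arm estimate or interval for any safety variable

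*Protocol*

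**What the plan says.** **Objective.** Section 6.1 states: "The primary objective is to compare the safety and efficacy of 2 concentrations of trifarotene cream HE1 versus vehicle". The objectives row of the Synopsis (2.1) has the same content. Section 7.1 says that the randomised period "is designed to compare the safety of 2 doses of trifarotene cream HE1 with that of vehicle in the treatment of LI", and Section 5.3 opens a sentence with "Although the primary objective of this study is safety in the patient population with LI".

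**Safety analysis.** Section 13.1.6 states: "No formal inferential analyses will be conducted for safety variables in either period". The same sentence stands in the Amendment 2 text and in the later text of Section 13 that counts in days and mentions COVID-19.

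**Adverse events.** Section 13.1.6.2 says: "The number and percentage of subjects with AEs will be displayed by each treatment group in the Double-blind Period", by system organ class and preferred term. It adds summaries by severity and by relationship to product, and then: "Serious adverse events and AEs resulting in discontinuation of IP will be summarized separately in a similar manner".

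**Other safety variables.** Local tolerability is summarised by period, arm and visit (13.1.6.1). Laboratory values and vital signs get descriptive statistics and shift tables (13.1.6.3, 13.1.6.4). The ECG section announces a comparison of QT results, but the method it gives is summary statistics by group and visit (13.1.6.5).

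**Events of special interest.** Section 11.3.1 designates local application-site adverse events. Section 11.2.1 requires every application-site reaction to be recorded as an adverse event.

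**Efficacy, for contrast.** Section 13.1.4.2 plans odds ratios with 95% intervals, and differences in proportions with 95% intervals and P values.

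**The concern.** One primary objective has two halves. The efficacy half gets an estimated contrast with its uncertainty; the safety half gets columns of arm-level summaries and no stated contrast. Whoever writes the report must judge by eye whether each concentration does worse than vehicle.

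Local irritation is where this matters most. Section 5.2 reports that irritation in healthy volunteers forced a reduction in application frequency, and Section 7.1 says that local tolerability of this formulation in lamellar ichthyosis is unknown. With about 40 subjects per arm, a sizeable excess can arise by chance, and a small observed excess can be compatible with a much larger one. If the report states neither the difference nor its imprecision, an excess that has not been excluded may be read as reassurance, or a chance excess as a signal.

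**Working it through.** **1. Is there a figure to reproduce?** No. The protocol states no expected adverse event rate, no target difference and no precision for safety. The power statement in Section 13.2 rests on efficacy success rates and is not an input here.

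**2. Objective against plan.**

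| Part of the primary objective | Display by arm | Difference from vehicle | 95% interval |
|---|---|---|---|
| Efficacy, primary endpoint (13.1.4.2) | yes | yes | yes |
| Adverse events (13.1.6.2) | yes | not specified | not specified |
| Local tolerability (13.1.6.1) | yes | not specified | not specified |
| Laboratory values, vital signs (13.1.6.3, 13.1.6.4) | yes, with shift tables | not specified | not specified |
| ECG, QT (13.1.6.5) | yes | not specified | not specified |
| Physical examination (13.1.6.6) | yes | not specified | not specified |

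**3. Can the key proportion be read from the planned tables?** Application-site reactions are recorded as adverse events, so they appear by arm under their preferred terms. One subject may have several terms, so the preferred-term rows cannot be added to give the number of subjects with at least one application-site event. Section 13 does not name that number as an output. Subjects with any adverse event, and with events leading to discontinuation, are covered by the planned tables.

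**4. What an interval would add.** Arm size: 120 subjects randomised 1:1:1 (Section 13.2), so 120/3 = 40 per arm. The event counts below are assumptions, since the protocol gives none.

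Formula (Newcombe): with Wilson 95% limits (l1, u1) for the active proportion p1 and (l2, u2) for the vehicle proportion p2, and d = p1 - p2,

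- lower limit = d - sqrt[(p1 - l1)² + (u2 - p2)²]
- upper limit = d + sqrt[(u1 - p1)² + (p2 - l2)²]

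Worked case, 16/40 against 8/40, in percentage points:

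- Wilson limits: 26.35 to 55.40 (active) and 10.50 to 34.76 (vehicle); d = 40 - 20 = 20
- lower: 20 - sqrt(13.65² + 14.76²) = 20 - 20.1 = -0.1
- upper: 20 + sqrt(15.40² + 9.50²) = 20 + 18.1 = 38.1

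| Active | Vehicle | Difference (points) | 95% interval |
|---|---|---|---|
| 16/40 | 8/40 | 20 | -0.1 to 38.1 |
| 12/40 | 4/40 | 20 | 2.3 to 36.6 |
| 20/40 | 12/40 | 20 | -1.4 to 39.0 |
| 4/40 | 4/40 | 0 | -14.4 to 14.4 |
| 3/40 | 0/40 | 7.5 | -2.5 to 19.9 |

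For a single arm with no events, the exact two-sided 95% upper limit is 1 - 0.025^(1/40) = 8.8%.

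Equal observed rates of 10% remain compatible with an excess of about 14 points. Three events against none remain compatible with an excess of about 20 points. Both facts bear directly on the stated objective, and no planned output states them.

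**The case against.** The case on the other side has several parts.

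- **Descriptive safety reporting is usual in phase 2.** The sample size rests on efficacy, and a randomised display by arm is itself a comparison. This stands to the extent that no test is called for. It does not explain why one half of a primary comparison gets an estimate and the other does not.
- **This is detail for the analysis plan.** Section 13 calls itself a summary, and a risk-difference column is ordinary table content. This stands in full for a separate table of events of special interest. It stands only in part for the estimates. Sections 13.1.4.5 and 13.1.5.1 pass details to the analysis plan explicitly; Section 13.1.6 instead sets a restriction without saying whether intervals fall under it.
- **The counts determine the interval.** True wherever the count is reported, so a reader could calculate it. The plan still does not report it, and for any application-site event the count itself is not a named output.
- **Six intervals would be wide and unadjusted.** True: the first two rows of the table are 38.2 and 34.3 points wide. That width is the information a reader needs.
- **Other safeguards exist.** The monitoring board reviews unblinded safety data (Section 12), and subject-level stopping rules apply (9.4.1). These protect subjects during the trial; they do not supply the final comparison.

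A reader might also infer that the events of special interest are never tabulated. The protocol does not support that. They are recorded as adverse events, shown by arm by class and term, covered by the summaries by severity and relationship, and their signs are summarised by arm and visit as local tolerability.

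**Conclusion.** The point holds as a mismatch between a primary objective worded as a comparison and a safety plan that specifies no between-arm estimate. Its weight is that of a cheap improvement. It would be too strong to say that the safety analysis is invalid, or that the protocol forbids intervals: the sentence in Section 13.1.6 can be read as excluding hypothesis tests only, and descriptive intervals are compatible with that reading.

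On size, an observed 20-point excess at 40 per arm carries an interval roughly 34 to 40 points wide under the assumed rates. Those rates are illustrations. The finding itself rests on the text alone.

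On versions, the objectives section that belongs to the later text of Section 13 is not among the pages at hand. The mismatch does not depend on combining versions, because Sections 6.1 and 13.1.6 of Amendment 2 show it by themselves.

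**What to change.** In Section 13.1.6, state that for the Double-blind Period each concentration will be described against vehicle by the difference in the proportion of subjects, with a 95% interval (Newcombe, for example), for three outcomes:

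1. any application-site adverse event, as designated in Section 11.3.1
2. any treatment-emergent adverse event
3. adverse events leading to discontinuation of the product

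In the same place, clarify that the exclusion of formal inference means that no hypothesis tests are done on safety variables. A separate table of events of special interest may be left to the analysis plan.

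The cost is a sentence or two and one or two tables from data already collected. The downside is 3 outcomes × 2 concentrations = 6 wide intervals without multiplicity adjustment, so they should be labelled descriptive and not read for whether they exclude zero. If the sponsor prefers purely by-arm reporting, rewording the safety part of the objective as a description would also remove the mismatch, but the reader would get less information.

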13.1.6.1 Local Tolerability

During all clinic visits, the investigator will assess local tolerability (stinging/burning, pruritus, or erythema on 0-3 scales [none, mild, moderate, severe]) for each treated body area (chest/abdomen, back, arms, legs, and face/neck). Descriptive summaries will be presented by period, treatment group, and visit.

